4.0 MATERIAL AND METHODS

4.1 Study Design: This is an open-label, non-interventional protocol testing a diagnostic device for the characterization of chemotherapy induced peripheral neuropathy. Patients will be stratified into Group A or Group B after completing the pain questionnaires. *There is no difference in testing protocols between these groups.*

4.2 Study Calendar:

| | Visit | Screening | 1 | 2 |
|---------------|--------------------------------------|-----------------------|--|---|
| | Time Points | -14 days from Visit 1 | 9 weeks from C1D1 of chemo (+/-1 week) | 21 weeks from C1D1 of chemo (+/-2 week) |
| Action | Screening and Consent | X | | |
| | Eligibility | X | | |
| | Demographics | X | | |
| | Medical History | X | | |
| | Cancer History | X | | |
| | Con Meds | X | X | X |
| | Cumulative dose of each chemotherapy | | X | X |
| | Pain Scale | X | X | X |
| | Neuropathic Pain Questionnaire (NPQ) | | X | X |
| | Headache Assessment | X | X | X |
| | DLss Testing | | X | X |

Note that the dose of platinum and/or taxane will be determined by the treating oncologist. No decisions about total dose, dose delays, escalations, or reductions will be made based on testing in this protocol.

4.3 Duration of Participation/Criteria for End of Study:

Patients will be asked to undergo testing on 2 separate days separated by approximately 10-15 weeks. Each study day is anticipated to take no longer than 2 hours.

Patients will be followed until event that occurs first:

- second DLss testing, which will occur 21 weeks +/- 2 weeks after their first dose of chemotherapy for ovarian cancer
- subject withdraws from study
- subject enters hospice
- subject dies
- PI or study staff determine continued participation is detrimental to the patient
- Study is terminated by the investigators or sponsor

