3.3 Enrollment

The target enrollment for this study is 25 patients with painful neuropathy symptoms (Group A) that develop during chemotherapy and 25 patients without painful symptoms during chemotherapy treatment (Group B). Final group assignment takes place on study day 1 when the patient takes a pain questionnaire. There are no differences in study activities between Group A and B. The Stanford Women's Cancer Center sees about 150 new cases of ovarian cancer per year, therefore we believe will able to complete enrollment in 12 months. Patients will be stratified into painful versus painless group based on their first pain assessment inventory. Based on the incidence of painful versus painless neuropathy, we anticipate that Group B will complete enrollment first. Should enrollment in Group A be very slow, our team will consider advertising outside of the Stanford Women's Cancer Center. An additional approach is to increase enrollment in Group B and apply an "unbalanced" design which would increase the number of patients in Group B, but still ensure statistical power of 80%. For example, if only 18 patients with pain are identified, enrolling 39 patients without pain will maintain 80% power. If this step is needed, we will amend the IRB as well as this application. Additionally, we will apply for a no-cost extension to the NIH SBIR that is funding the project.

We understand that patients participating in non-interventional, longitudinal, clinical studies may not follow up for a variety of reasons. To address possible drop out, patients will receive higher compensation for participation in the second test, 75 dollars for the first, 125 dollars for the second. A commonly anticipated drop-out rate is 20% (45), leaving us with approximately 40 patients who we anticipate will complete both time points within the study timeframe. However, it is possible that patients in pain (Group A) may be more likely to follow up with the second test, which would help preserve the power of the study.

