4.4 Description of Study Activities

Screening within 14 days prior to the first DLss testing:

- Written informed consent must be obtained from the subject prior to performance of any study-specific tests or evaluations. Subjects must be consented to undergo the pain questionnaires and DLss testing. If patient remains in active screening, consent does not need to be repeated if more than 14 days from DLss testing.

- Subjects will be asked to call and reschedule testing appointments if they have pain ≥ 50 on a scale of 0-100 (0=no pain, 100= worst pain imaginable) on the day of the scheduled test
- Eligibility criteria
- Headache assessment: assess for chronic daily headache or headache more than 14 days of the last month
- Demographics: birth date, race/ethnicity, and gender at birth.
- Medical history
- Cancer history including prior chemotherapy for malignancy
- Prior and concomitant therapy (including all previous therapy for malignancy, radiation, surgery, concomitant medications including OTC drugs, herbs, and St. John's Wort) taken in the week prior to DLss testing.

Study Visit 1 (9 weeks +/- 1 week from cycle 1, day 1 of chemotherapy)

- Concomitant medications taken in the last week
- Cumulative dose of each chemotherapy (As calculate by dose in mg x number of doses)
- Headache assessment as above
- Pain Questionnaires:
 - o Numeric Pain Scale: Patients will be asked to rate their overall pain on a scale from 0 to 100, where 0 is no pain and 100 is the worst imaginable pain (27, 46). Patients who are experiencing pain ≥ 50 despite intervention will be asked to reschedule testing. If needed, the patient will be referred to their MD for standard of care pain control measures. Painful neuropathy will be defined as pain scale ≥ 10 .
 - o Neuropathic Pain Questionnaire (NPQ):

This test will take less than 6 minutes to complete.

The NPQ was initially validated in 528 chronic pain patients from several clinics. This test is able to differentiate neuropathic pain patients from non-neuropathic pain patients. The NPQ may be used for the initial screening of neuropathic pain patients. It also has the ability to provide a quantitative measure for the descriptors important in the diagnosis and assessment of neuropathic pain. Consequently, it can be used for monitoring of neuropathic pain treatments and as an outcome measure.

For additional details: <https://www.ncbi.nlm.nih.gov/pubmed/12966256>.
A copy is included as **Appendix C**.

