- DLss testing per the following protocol

We anticipate the total testing will take 30 minutes or less

 - 1) Subjects will be comfortably seated in a treatment recliner or in a gurney in a private room in the Stanford CTRU. Patient and the examiner will wear safety goggles. The door will be closed. The areas of skin to be tested will be shaved to avoid differences in light absorption and heating, because stimulation is non-contact; but strong pigmentation spots, tattoos, and moles will be avoided.

- 2) Patients will be reminded that if pain becomes too difficult for them to tolerate, they can stop the testing at any time.
- 3) The skin on the dorsum of the foot will be marked with a pen denoting 10mmx10mm squares.
- 4) The skin temperature will be monitored by infrared thermometer before the test and every 5 minutes during testing. If skin temperature is below 33 C, the skin tissue will be heated with warmed towels and maintained to keep temperature +/- 0.5 °C.
- 5) Each patient will have an A and C fiber stimulation. Stimulation will be performed on the dorsum of the foot using stimulation previously published parameters to elicit “burning pain,” which is from activation of C-fibers and “pinprick” pain from A-fibers:
 - A_δ fiber protocol*: 60-millisecond duration, 980-nm stimuli, 1-mm diameter stimuli
 - C fiber protocol*: 2-second duration, 980-nm stimuli, 5-mm diameter stimuli
- 6) Stimulation will begin at 600mA±2 current (if sensation is felt at 600mA±2, go down two levels or 400mA±2) and increased at 100mA±2 increments until the subject identifies the stimulation as painful. The current will be increased up to a maximum of 1650 mA for the C-fiber protocol and to a maximum of 3500 mA for the A_δ-fiber protocol. In rare cases, patients may have pain thresholds that exceed the maximum skin temperature considered safe. For these patients, we will use the maximum safe stimulus level (3500 mA for the A_δ fiber, 1650 mA for the C fiber) to calculate the A_δ:C ratio. For subsequent runs, start at the highest level that do not evoke sensation from prior run (if sensation is felt at that level, go down two levels or 200mA ±2)

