- 7) The pain threshold will be obtained using the “method of levels”, using a series of ascending stimulation from energy that does not evoke sensation (600mA) and increasing by steps of 100mA until the last sensation is recorded as a 30-40 on the 0-100 pain scale. (0= no sensation, 10= definite sensation/pain, 100 worst imaginable pain). The procedure will be repeated three times and the pain threshold will be defined as averaging the readings of the 3 successive stimulations. The selected current will be applied 4 times. At this current, we expect to produce pain 50% of the time, and no pain 50% of the time.
- 8) The area of stimulation will be moved by 5 millimeters between each stimulation according to the grid (see #3).

Study Visit 2 (21 weeks +/- 2 weeks after first dose of chemotherapy for ovarian cancer)

- Concomitant medications as above
- Cumulative chemotherapy dose as above
- Headache assessment as above
- Pain inventories as above
- DLss testing as described above

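### Nothing in the protocol keeps the DLss examiner from knowing the patient's pain score or group while eliciting the patient-reported threshold behind the primary comparison

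*Combined protocol and SAP*

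**What the plan says.** Section 4.1 describes the design: "This is an open-label, non-interventional protocol testing a diagnostic device". The same section says that "Patients will be stratified into Group A or Group B after completing the pain questionnaires", and section 3.3 fixes the timing: "Final group assignment takes place on study day 1 when the patient takes a pain questionnaire". Section 4.4 lists the numeric pain scale and the Neuropathic Pain Questionnaire (NPQ) ahead of DLss testing at Visit 1, and Visit 2 follows the same list.

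The numeric scale does two jobs in section 4.4. Patients scoring 50 or more "despite intervention will be asked to reschedule testing". On the same 0 to 100 scale, "Painful neuropathy will be defined as pain scale" of 10 or more.

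The threshold is elicited face to face. Step 1 of the DLss procedure names the operator only by role: "Patient and the examiner will wear safety goggles". Step 6 raises the current "until the subject identifies the stimulation as painful". Step 7 describes "increasing by steps of 100mA until the last sensation is recorded as a 30-40 on the 0-100 pain scale", and the result is averaged over three runs. Starting current, increments, step-down rules and maxima are all specified.

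Section 3.1 gives coordinators (or a physician) the consent task. Section 6.2 places the written inventories in the coordinators' offices. Appendix A has the eligibility checklist, which carries the Group A/B criterion, completed before registration and verified by the coordinator, the treating physician and an independent reviewer. No section says who gives the questionnaires on the test day, who operates the DLss, or whether the operator sees the scores.

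**The concern.** The primary outcome in section 5.1.1 is the difference in A-delta:C threshold ratio between the painful and painless groups. Section 5.2 states a directional expectation, a higher ratio in the painful group. Section 1.0 gives its form: a raised A-delta threshold with C thresholds intact. An examiner who knows the group and the expectation may, without intending it, prompt differently, accept a rating sooner or later, or lean on one of the two stopping descriptions rather than the other.

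Such an effect would line up with group membership, so the t-test could not tell it from a real difference, and no later adjustment would separate the two. It would also enter Aim 2, where the Visit 1 ratio is used to predict pain at Visit 2.

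**Working it through.** **1. Can the examiner know the group?** Three elements of the protocol, taken together:
- Group is assigned from a questionnaire on the day of the first test (sections 3.3 and 4.1).
- Someone must see the numeric score before testing, to apply the limit of 50. The same score, read against 10, indicates painful neuropathy (section 4.4).
- No masking statement appears, and the examiner is not separated from whoever collects the scores. The checklist in Appendix A is a second route to the group.

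So the examiner may know. The documents do not establish that the examiner does know.

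**2. Where could knowledge act?** The current levels are prescribed and three runs are averaged, which limits discretion. What remains is verbal interaction and the stop point. Step 6 stops when the patient calls the stimulus painful. Step 7 stops at a rating of 30-40, on a scale where 10 already denotes definite sensation or pain. These two descriptions differ and need to be reconciled.

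**3. The plan's own figure.** Inputs from section 5.3: n = 25 per group, log-scale SD 0.33, detectable ratio 1.31. Section 5.2 gives a two-sided t-test. Alpha is not stated; 0.05 is assumed.
- Standard error of the difference = 0.33 × √(2/25) = 0.0933.
- Noncentrality = ln(1.31)/0.0933 = 0.2700/0.0933 = 2.89, with 48 degrees of freedom and critical value 2.011.
- Power = 80.9%, which agrees with the stated 80%.

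**4. Illustration of a spurious shift.** Take no true difference and a systematic multiplicative shift f in Group A ratios. The rejection probability uses the same noncentral t with noncentrality ln(f)/0.0933.

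| Shift f | ln(f) | Noncentrality | False-positive rate |
|---|---|---|---|
| 1.00 | 0 | 0 | 5.0% |
| 1.03 | 0.0296 | 0.32 | 6.1% |
| 1.05 | 0.0488 | 0.52 | 8.1% |
| 1.10 | 0.0953 | 1.02 | 17.0% |

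**5. What these shifts mean in current.** The documents give no typical thresholds, so the levels here are assumptions.
- One 100 mA step up on the A-delta threshold alone: 1100/1000 = 1.10 (17.0%), 2100/2000 = 1.05 (8.1%), 3100/3000 = 1.033 (6.4%).
- One extra step in only one of three averaged runs at 1000 mA moves the mean by 33 mA: 1.033 (6.4%).
- One extra step on both fibers from 2000 and 1000 mA: (2100/1100)/(2000/1000) = 0.955, a fall of 4.5%, against the hypothesis.

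**The case against.** The strongest reply is that the procedure leaves the examiner little to decide. Levels, increments and limits are set, three runs are averaged, section 4.1 says testing does not differ between groups, and the patient's own report ends each series. This stands as a limit on how much bias is plausible. It does not remove the concern, because the report is given verbally to the examiner and the stop point is described in two ways.

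A second reply is that the outcome is a within-patient ratio, so behavior that moves both thresholds partly cancels and can even run against the hypothesis. That also stands. The concern is confined to influence that differs between the two fibers, which is the form the stated expectation takes.

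Third, a 10% shift needs a full extra step in every averaged run, on average across Group A, in one fiber type, at a low threshold. That is fair, and the smaller rows of the table deserve as much attention.

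Fourth, patients know their own pain status and cannot be masked, and Appendix A calls this a feasibility study. Both are true. Examiner masking removes one source of bias, not all of them.

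A reader might infer from the open-label description that the examiner does know the group. The label alone does not say so, and list order in section 4.4 is not a stated sequence. The support is the same-day grouping, the pre-test pain check and the absence of any masking text. A reader might also infer that the named coordinators could hold back the forms without any staffing cost. The documents give them consent, eligibility verification and storage of the forms, but no test-day duties, and they give no cost figure.

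**Conclusion.** The point holds as a gap in design. The protocol, followed as written, allows the examiner to know pain status while eliciting a subjective threshold, and this bears directly on the primary contrast. The size of any resulting bias is unknown. The false-positive rates of about 6%, 8% and 17% for shifts of 3%, 5% and 10% are sensitivity figures. They rest on 25 per group, log SD 0.33, an assumed two-sided alpha of 0.05 and no true difference. They do not show that bias of any such size will occur. The change should be made because it must be in place before data are collected and alters neither sample size nor testing parameters.

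**What to change.** Add to section 4.4, for both visits:
- The patient completes the pain scale and NPQ on paper. A staff member other than the DLss examiner (for example a coordinator of the kind named in section 3.1) collects them, applies the protocol's existing pain check, and tells the examiner only *proceed* or *reschedule*.
- Until both thresholds are entered in OnCore, the examiner does not see the pain scores, the NPQ, the Group A/B field of the eligibility checklist or the pain-medication list.
- Patients are asked not to discuss symptoms during testing.

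The text should also name who performs each task, and the stop points in steps 6 and 7 should be reconciled.

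The cost is minor coordination on the test day. Masking will be imperfect if a patient mentions symptoms. The sponsor should confirm that existing roles suffice. If one person must do both tasks, the patient can seal the forms and report only whether the existing pain limit is met.

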4.4 Description of Study Activities

Screening within 14 days prior to the first DLss testing:

- Written informed consent must be obtained from the subject prior to performance of any study-specific tests or evaluations. Subjects must be consented to undergo the pain questionnaires and DLss testing. If patient remains in active screening, consent does not need to be repeated if more than 14 days from DLss testing.

- Subjects will be asked to call and reschedule testing appointments if they have pain ≥ 50 on a scale of 0-100 (0=no pain, 100= worst pain imaginable) on the day of the scheduled test
- Eligibility criteria
- Headache assessment: assess for chronic daily headache or headache more than 14 days of the last month
- Demographics: birth date, race/ethnicity, and gender at birth.
- Medical history
- Cancer history including prior chemotherapy for malignancy
- Prior and concomitant therapy (including all previous therapy for malignancy, radiation, surgery, concomitant medications including OTC drugs, herbs, and St. John's Wort) taken in the week prior to DLss testing.

Study Visit 1 (9 weeks +/- 1 week from cycle 1, day 1 of chemotherapy)

- Concomitant medications taken in the last week
- Cumulative dose of each chemotherapy (As calculate by dose in mg x number of doses)
- Headache assessment as above
- Pain Questionnaires:
 - o Numeric Pain Scale: Patients will be asked to rate their overall pain on a scale from 0 to 100, where 0 is no pain and 100 is the worst imaginable pain (27, 46). Patients who are experiencing pain ≥ 50 despite intervention will be asked to reschedule testing. If needed, the patient will be referred to their MD for standard of care pain control measures. Painful neuropathy will be defined as pain scale ≥ 10 .
 - o Neuropathic Pain Questionnaire (NPQ):

This test will take less than 6 minutes to complete.

The NPQ was initially validated in 528 chronic pain patients from several clinics. This test is able to differentiate neuropathic pain patients from non-neuropathic pain patients. The NPQ may be used for the initial screening of neuropathic pain patients. It also has the ability to provide a quantitative measure for the descriptors important in the diagnosis and assessment of neuropathic pain. Consequently, it can be used for monitoring of neuropathic pain treatments and as an outcome measure.

For additional details: <https://www.ncbi.nlm.nih.gov/pubmed/12966256>.
A copy is included as **Appendix C**.
- DLss testing per the following protocol

We anticipate the total testing will take 30 minutes or less

 - 1) Subjects will be comfortably seated in a treatment recliner or in a gurney in a private room in the Stanford CTRU. Patient and the examiner will wear safety goggles. The door will be closed. The areas of skin to be tested will be shaved to avoid differences in light absorption and heating, because stimulation is non-contact; but strong pigmentation spots, tattoos, and moles will be avoided.

- 2) Patients will be reminded that if pain becomes too difficult for them to tolerate, they can stop the testing at any time.
- 3) The skin on the dorsum of the foot will be marked with a pen denoting 10mmx10mm squares.
- 4) The skin temperature will be monitored by infrared thermometer before the test and every 5 minutes during testing. If skin temperature is below 33 C, the skin tissue will be heated with warmed towels and maintained to keep temperature +/- 0.5 °C.
- 5) Each patient will have an A and C fiber stimulation. Stimulation will be performed on the dorsum of the foot using stimulation previously published parameters to elicit “burning pain,” which is from activation of C-fibers and “pinprick” pain from A-fibers:
 - A_δ fiber protocol*: 60-millisecond duration, 980-nm stimuli, 1-mm diameter stimuli
 - C fiber protocol*: 2-second duration, 980-nm stimuli, 5-mm diameter stimuli
- 6) Stimulation will begin at 600mA±2 current (if sensation is felt at 600mA±2, go down two levels or 400mA±2) and increased at 100mA±2 increments until the subject identifies the stimulation as painful. The current will be increased up to a maximum of 1650 mA for the C-fiber protocol and to a maximum of 3500 mA for the A_δ-fiber protocol. In rare cases, patients may have pain thresholds that exceed the maximum skin temperature considered safe. For these patients, we will use the maximum safe stimulus level (3500 mA for the A_δ fiber, 1650 mA for the C fiber) to calculate the A_δ:C ratio. For subsequent runs, start at the highest level that do not evoke sensation from prior run (if sensation is felt at that level, go down two levels or 200mA ±2)
- 7) The pain threshold will be obtained using the “method of levels”, using a series of ascending stimulation from energy that does not evoke sensation (600mA) and increasing by steps of 100mA until the last sensation is recorded as a 30-40 on the 0-100 pain scale. (0= no sensation, 10= definite sensation/pain, 100 worst imaginable pain). The procedure will be repeated three times and the pain threshold will be defined as averaging the readings of the 3 successive stimulations. The selected current will be applied 4 times. At this current, we expect to produce pain 50% of the time, and no pain 50% of the time.
- 8) The area of stimulation will be moved by 5 millimeters between each stimulation according to the grid (see #3).

Study Visit 2 (21 weeks +/- 2 weeks after first dose of chemotherapy for ovarian cancer)

- Concomitant medications as above
- Cumulative chemotherapy dose as above
- Headache assessment as above
- Pain inventories as above
- DLss testing as described above

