5.0 STATISTICAL CONSIDERATIONS

5.1 Outcome Measurements

5.1.1 Outcome Measure for Aim 1

The primary outcome measure of this study is the difference in the “A δ :C pain threshold ratio” for patients with a painless response to chemotherapy versus painful neuropathy, as measured using the DLss.

The “A δ :C pain threshold ratio” is calculated using the A δ -fiber and C-fiber pain thresholds determined using the protocol outlined in **section 4.4**.

Each patient will have 2 testing sessions:

- 1) 9 weeks +/- 1 week from cycle 1, day 1 of chemotherapy
- 2) 21 weeks +/- 2 weeks after first dose of chemotherapy for ovarian cancer

This is not a safety outcome.

5.1.2 Outcome Measure for Aim 2

The second outcome measure of this study is the correlation between the “A δ :C pain threshold ratio” and the development of pain.

We will generate a Spearman correlation coefficient for the “A δ :C pain threshold ratio” obtained at the first testing session and the presence or absence of pain at the time of the second test.

This is not a safety outcome.

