5.2 Analysis plan

The A δ :C pain threshold ratio will be recorded for each eligible and evaluable patient for both time points. We will calculate the average value of this parameter for each group (A and B) on a logarithmic scale. Then we will use a standard statistical two side t-test to compare the “A δ :C pain threshold ratio” in the painless CIPN group to the painful CIPN group. We hypothesize that the painful CIPN group will have statistically significantly higher value “A δ :C pain threshold ratio” than those without.

To assess whether the “A δ :C pain threshold ratio” predicts future painful or painless CIPN, we will conduct logistic regression analysis of the binary pain value (pain or no pain) at the time of the second testing (independent variable) on the “A δ :C pain threshold ratio” at the time of the first testing (dependent variable). It will allow us to estimate whether the “A δ :C pain threshold ratio” predicts the chances of a patient to develop pain.

As an exploratory analysis, we will explore if the “A δ :C pain threshold ratio” obtained at

the first testing session predicts an increase in the numeric pain scale at the second testing session.

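### Read literally, the plan takes Aim 2 pain at a second laser test that is postponed at pain ≥ 50, so a patient in persistent severe pain drops out of the Aim 2 analyses

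*Combined protocol and SAP*

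**What the plan says.** The Numeric Pain Scale item in section 4.4, written under Visit 1, asks for overall pain from 0 to 100. It then sets two rules: "Patients who are experiencing pain ≥ 50 despite intervention will be asked to reschedule testing" and "Painful neuropathy will be defined as pain scale ≥ 10". The Visit 2 list in the same section carries the item over with "Pain inventories as above" and states no exception. The screening list in 4.4 also applies the 50-point rule to testing appointments in the plural, whereas exclusion 3.2.4 is limited to the first DLss test.

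The outcomes are tied to the test. Section 5.1.2 correlates the first-session ratio with "the presence or absence of pain at the time of the second test". Section 5.2 regresses on the "binary pain value (pain or no pain) at the time of the second testing" and, as an exploratory analysis, asks whether the first ratio "predicts an increase in the numeric pain scale at the second testing session".

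Section 4.3 ends follow-up at the "second DLss testing, which will occur 21 weeks +/- 2 weeks after their first dose of chemotherapy for ovarian cancer", or earlier for withdrawal, hospice, death, a staff decision that continuing is detrimental, or study termination. The calendar in 4.2 lists Pain Scale, NPQ and DLss Testing as separate rows at Visit 2. Section 5.2 analyses evaluable patients without defining the term and gives no rule for a second test that is late or never done.

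**The concern.** Postponing laser stimulation for a patient in severe pain is sensible. The difficulty is which pain rating is then analysed. If it is the one taken when the second test is done, it comes from a day selected because pain was below 50. If no such day comes within the window, there is no second test to supply a rating.

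Aim 2 asks whether the Visit 1 ratio predicts who has pain at Visit 2. A patient lost this way is lost because of her outcome, and always from the side the plan's cut-off calls painful. The observed share with pain is then too low. If the ratio rises with severity, the odds ratio is also pulled toward 1. In the exploratory analysis, large rises in the score cannot appear. None of this loss is necessary, because the Aim 2 prediction needs only the Visit 1 ratio and Visit 2 pain, not a second laser test.

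**Working it through.** **Step 1: the plan's own figures.** Section 5.3 gives 25 per group, a 1.31-fold ratio and a log-scale SD of 0.33. With delta = ln(1.31) = 0.270 and two-sided alpha 0.05 (the level is assumed; the plan does not state it), the noncentral t gives 80.9% power, against the stated 80%. Section 3.3 expects 20% drop-out, "leaving us with approximately 40 patients who we anticipate will complete both time points within the study timeframe": 50 × (1 − 0.20) = 40. The plan gives no power for Aim 2 and no frequency of pain ≥ 50 at Visit 2.

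**Step 2: what the literal text does at Visit 2.**
- First rating below 50: tested as planned, no problem.
- First rating ≥ 50, later below 50 and tested: the binary outcome is still pain provided she rates at least 10. Her score can be at most 49. For example, 40 at Visit 1 and 80 at the first Visit 2 contact is a true rise of 80 − 40 = 40, but the largest rise that can be analysed is 49 − 40 = 9.
- Rating ≥ 50 throughout weeks 19 to 23 (21 ± 2): no second test, so no rating at a second test.

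**Step 3: number lost and pain share.** Let p be the share at ≥ 50, f the fraction of them never retested, and 0.50 the true share in pain (assumed). Expected loss among 40 is 40 × f × p. For p = 5% / 10% / 20% this is 0.5 / 1 / 2 patients with f = 0.25 and 1 / 2 / 4 with f = 0.5. The observed pain share is (0.50 − f p) / (1 − f p). With f = 0.5 and p = 0.10 it is 0.45 / 0.95 = 0.474.

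**Step 4: power and odds ratio.** Simulation with n = 40 and 20,000 runs per case. Latent Visit 2 pain is normal and has correlation 0.4 with the Visit 1 log ratio (assumed); the test is a logistic likelihood-ratio test at two-sided 0.05. Cells show power, then median odds ratio per SD.

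| Never retested, of those at ≥ 50 | p = 5% | p = 10% | p = 20% |
|---|---|---|---|
| None | 55.9%, 2.11–2.12 | 56.3%, 2.11–2.12 | 56.4%, 2.11–2.12 |
| A quarter | 53.9%, 2.08 | 52.8%, 2.07 | 50.9%, 2.06 |
| Half | 51.6%, 2.05 | 48.9%, 2.02 | 44.4%, 1.99 |
| All (extreme) | 47.3%, 2.00 | 40.6%, 1.92 | 29.2%, 1.79 |

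The power loss is 2.0 / 3.5 / 5.5 points with a quarter lost and 4.3 / 7.4 / 12.0 points with half lost. With correlation 0.5, power is 78% with none lost and 73.5% / 70.1% / 64.5% with half lost.

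**Step 5: if these losses already sit inside the planned 20% drop-out** (50 tested at Visit 1, 10 non-completers including the patients in question; 12,000 runs). With a quarter lost, power is 54.8% / 53.0% / 52.3% as written and 57.2% / 57.2% / 58.4% with the rating kept. With half lost it is 52.3% / 50.0% / 47.0% against 57.8% / 58.8% / 61.0%. The widest gap, 14.0 points, partly reflects the larger analysed number once ratings are kept (about 45 instead of 40).

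**Step 6: the cap in the exploratory analysis.** If every score ≥ 50 is replaced by 49, the slope on the Visit 2 score is 0.92 / 0.83 / 0.68 of its uncapped value. The correlation hardly changes (0.367 to 0.367, 0.362 to 0.361, 0.358 to 0.353). For the increase from Visit 1, with assumed correlations of 0.3 (ratio with Visit 1 pain) and 0.5 (Visit 1 with Visit 2 pain), the slope is 0.84 / 0.74 / 0.61 of its uncapped value.

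**The case against.** The other side has several fair points.

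- **The outcome may be defined by time.** Section 5.1.1 describes the second session as a window, and the calendar schedules the pain instruments apart from the laser test. A rating of 50 or more may therefore be on file and could be scored as pain. A reader might infer that such a patient has no outcome data at all; the documents do not support that. What stands is that no sentence makes that rating the outcome, and a patient who telephones to reschedule may never give one in clinic.
- **The rule is written under Visit 1.** The Visit 2 cross-reference could mean the instruments only. The plural appointments in the screening text and the lack of an exception make carry-over the more natural reading, but it remains a reading.
- **The end-of-follow-up list.** A reader might infer that 4.3 leaves her wholly uncovered. The entries for withdrawal and for a staff decision that continuing is detrimental could apply. Neither says how to score her.
- **Overall pain is not neuropathic pain.** A reader might infer that every lost patient is a painful CIPN case. She meets the ≥ 10 wording, but the trigger is overall pain, and Group A eligibility rests on symptoms in fingers or toes scored on the NPQ.
- **The NPQ asks about usual pain.** It is not capped by the choice of test day, and the Aim 1 text determines pain from questionnaire and numeric scale together. The cap therefore concerns the numeric score only.
- **Few patients are likely to be affected.** The window is four weeks wide and patients can be referred for pain control, so the all-lost row is an extreme.

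**Conclusion.** The point holds as a mismatch between a sensible testing rule and an outcome anchored to the test. Followed literally, the plan removes patients from the Aim 2 prediction analyses because of their outcome, and truncates the exploratory score for those who are rescheduled. Its size cannot be computed from the documents. Under the assumptions in steps 3 and 4, with a quarter to half of the patients at ≥ 50 never retested, Aim 2 power falls by about 2 to 12 points and the odds ratio barely moves. If all are retested and still rate at least 10, the binary result is unchanged.

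A reader might infer that Aim 2 is seriously biased or that the primary comparison is compromised. The documents support neither. The number affected is unknown and probably small, the analyses concerned are secondary and exploratory, and Aim 1 is untouched if it uses Visit 1 data. The change is still worth making, because it costs almost nothing and settles in advance which rating counts.

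**What to change.** 1. In section 4.4, Visit 2, state that the Numeric Pain Scale and NPQ are completed at the first scheduled Visit 2 contact within 21 ± 2 weeks, in clinic or by telephone, whatever the rating, and that a rating of 50 or more postpones only the DLss test.
2. In sections 5.1.2 and 5.2, define the Aim 2 and exploratory pain outcomes from that first assessment, and keep the patient in these analyses even if the second DLss test is never done.

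The cost is one sentence in each of 4.4, 5.1.2 and 5.2, plus a telephone assessment for the few who reschedule by phone; the plan puts the NPQ at under six minutes. It adds no visit and no laser testing of anyone at 50 or more.

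There are three downsides. A few telephone ratings are mixed with clinic ratings. A non-neuropathic flare on that day may count as pain on the overall scale, which the NPQ from the same contact can be used to check. The Visit 2 ratio stays missing for patients never retested, so the part of Aim 2 that looks at change in the ratio is not helped.
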